#### 8.4.4.6 Vital signs

Pre-dose vital signs (pulse, systolic blood pressure, diastolic blood pressure, respiration rate and body temperature) will be obtained in accordance with the schedule provided in [Table 1](#).

Changes in vital signs variables between baseline and each subsequent scheduled assessment will be calculated. Baseline will be defined as the last value prior to the first dose of

randomized treatment. The change from baseline will be defined as the treatment period value minus the baseline period value. There will be no imputation for missing values.

Absolute values will be compared to the relevant reference range and classified as low (below range), normal (within range or on limits) or high (above range). All values (absolute and change) falling outside the reference ranges will be flagged.

Body mass index (BMI) will be calculated from the height (in meters) and weight (in kilograms) as follows:

$$\text{BMI} = \text{kg/m}^2$$

#### **8.4.5 Calculations or derivation of Pharmacokinetic and Immunogenicity variables**

Blood samples (processed to serum) for pharmacokinetic and immunogenicity assessments will be collected from all subjects at baseline prior to first IP administration at Visit 3, at multiple time points before IP administrations during the treatment period, and at selected time points in the follow-up phase of the study. Anti-drug antibodies assessments will be conducted utilizing a tiered approach (screen, confirm, titer). These validated methods are conducted using a bridging assay format and statistically determined floating screening assay cut point factor and confirmatory assay cut point. The minimal sample dilution is 1:13. Titer values are reported as the reciprocal of the highest dilution that yields a value above the cut point. Samples from pre-defined study time points that confirm positive for ADA will also be tested for neutralizing ADA/nAb activity. Both ADA and nAb will be summarized using descriptive statistics as described in Section 8.5.9.

#### **Pharmacokinetics and immunogenicity of tralokinumab:**

Tralokinumab serum concentrations will be tabulated by time along with descriptive statistics. Population PK modelling may also be performed to better characterize the PK of tralokinumab, but will be reported separately from the CSR.

The incidence rate of ADA to tralokinumab will be reported by tralokinumab treatment group. If possible and if relevant, the impact of ADA occurrence on the PK and PD and safety will be summarized in the CSR.

### **8.5 Methods for statistical analyses**

The main focus for the statistical analyses is to compare tralokinumab to placebo in the two pre-defined populations, all subjects and biomarker positive subjects, with regards to primary, key secondary, and safety objectives.

The analysis of the study endpoints will include all data captured during the 52-week double-blind treatment period. This includes data regardless of whether study treatment was prematurely discontinued or delayed, and/or irrespective of protocol adherence, unless the subject withdraws consent or assent to study participation. The statistical analyses will compare tralokinumab to placebo.

Summary data will be presented in tabular format by treatment. Categorical data will be summarized by the number and percentage of subjects in each category. Continuous variables for parametric data will be summarized by descriptive statistics including N, mean, SD, median, and range. All data will be listed. Data listings will be sorted by treatment and subject number.

All hypothesis testing will be reported using 2-sided tests. P-values will be rounded to 4 decimal places.

### 8.5.1 Testing strategy for primary and key secondary objectives

The pre-defined hierarchical testing strategy for testing of the primary and key secondary hypothesis in the primary populations described below, gives global strong control of the Type I error (FWER).

**Step 1:** The primary endpoint in the biomarker positive population will be tested two-sided at  $\alpha=0.05$

**Step 2:** If a significant treatment effect is shown with regards to the primary endpoint in the biomarker positive population in Step 1, then the key secondary endpoint, percent change from baseline in pre-dose/pre-BD FEV1 at Week 52 vs. placebo will be tested two-sided at  $\alpha=0.05$  within that population using the hierarchical testing approach. Otherwise, testing will stop. All subsequent results within the hierarchy will be declared non-significant.

**Step 3:** If a significant treatment effect is shown with regards to the key secondary endpoint percent change from baseline in pre-dose/pre-BD FEV1 at Week 52 vs. placebo in the biomarker positive population in Step 2, then the next key secondary endpoint, change from baseline in AQLQ(S)+12 at Week 52 vs. placebo will be tested two-sided at  $\alpha=0.05$  within that population using the hierarchical testing approach. Otherwise, testing will stop. All subsequent results within the hierarchy will be declared non-significant.

**Step 4:** If a significant treatment effect is shown with regards to the key secondary endpoint change from baseline in AQLQ(S)+12 at Week 52 vs. placebo in the biomarker positive population in Step 3, then the next key secondary endpoint, change from baseline in ACQ-6 at Week 52 vs. placebo will be tested two-sided at  $\alpha=0.05$  within that population using the hierarchical testing approach. Otherwise, testing will stop. All subsequent results within the hierarchy will be declared non-significant.

**Step 5:** If a significant treatment effect is shown with regards to the key secondary endpoint of change from baseline in ACQ-6 at Week 52 vs placebo in the biomarker positive population, then the key secondary endpoint of change from baseline in bi-weekly mean daily asthma symptom score at Week 52 vs placebo in the biomarker positive population and the primary endpoint in the all subjects population will be tested using a Bonferroni approach at significance  $\alpha$ . Hence, each of the two endpoints will be tested at significance level  $\alpha/2$  ( $=0.025$ ). If at least one significant treatment effect is shown at this step, testing will continue

to step 6. Otherwise, testing will stop. All subsequent results within the hierarchy will be declared non-significant.

**Step 6:** Percent change from baseline in pre-dose/pre-BD FEV1 at Week 52 vs. placebo in the all subjects population will only be tested if at least one significant treatment effect is shown at step 5. There are two different outcomes in Step 5 that could result in testing the hypothesis for FEV1:

- (a) If both comparisons in step 5 exhibits significance, then FEV1 in the all subjects population is testable and will be tested at significance level  $\alpha$  ( $=0.05$ ).
- (b) If only one of the hypotheses in step 5 exhibits significance, then FEV1 in the all subjects population is testable and will be tested at significant level  $\alpha/2$  ( $=0.025$ ).

**Step 7:** If a significant treatment effect is shown with regards to percent change from baseline in pre-dose/pre-BD FEV1 at Week 52 vs. placebo in the all subjects population then change from baseline in AQLQ(S)+12 at Week 52 vs placebo will be tested using the significance level used in step 6 ( $\alpha$  ( $=0.05$ ) if outcome (a) from Step 5, or  $\alpha/2$  ( $=0.025$ ) if outcome (b) from step 5). Otherwise, testing will stop. All subsequent results within the hierarchy will be declared non-significant.

**Step 8:** If a significant treatment effect is shown with regards to change from baseline in AQLQ(S)+12 at Week 52 vs placebo in the all subjects population then change from baseline in ACQ-6 at Week 52 vs placebo will be tested using the significance level used in step 7 ( $\alpha$  ( $=0.05$ ) if outcome (a) from Step 5, or  $\alpha/2$  ( $=0.025$ ) if outcome (b) from step 5). Otherwise, testing will stop. All subsequent results within the hierarchy will be declared non-significant.

**Step 9:** If a significant treatment effect is shown with regards to change from baseline in ACQ-6 at Week 52 vs placebo in the all subjects population then change from baseline in bi-weekly mean daily asthma symptom score vs placebo will be tested using the significance level used in step 8 ( $\alpha$  ( $=0.05$ ) if outcome (a) from Step 5, or  $\alpha/2$  ( $=0.025$ ) if outcome (b) from step 5). Otherwise, testing will stop. All subsequent results within the hierarchy will be declared non-significant.

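### The Step 5–9 test sequence controls the family-wise error but leaves half of alpha unused when only one Step 5 hypothesis is rejected and Steps 6–9 all succeed

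*Protocol*

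**What the plan says.** Section 8.5.1 starts from the full two-sided 5% level: "The primary endpoint in the biomarker positive population will be tested two-sided at" 0.05, and Section 8.5 adds "All hypothesis testing will be reported using 2-sided tests". Steps 2–4 pass that level down through FEV1, AQLQ(S)+12 and ACQ-6 in the biomarker positive population.

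Step 5 splits the level between the biomarker positive symptom score and the all-subjects exacerbation rate: "Hence, each of the two endpoints will be tested at significance level" 0.025. A single rejection of either opens the next step: "If at least one significant treatment effect is shown at this step, testing will continue".

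Steps 6–9 then test FEV1, AQLQ(S)+12, ACQ-6 and symptom score in all subjects. The level is 0.05 for the case "If both comparisons in step 5 exhibits significance" and 0.025 for the case "If only one of the hypotheses in step 5 exhibits significance". At Step 9 the symptom score "will be tested using the significance level used in step 8". No step follows, and no rule sends the level of Step 9 anywhere.

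The section describes the hierarchy as pre-defined and as controlling the family-wise error rate strongly.

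**The concern.** Suppose exactly one Step 5 hypothesis is rejected. Its 0.025 moves on to Step 6 and, if every test succeeds, through to Step 9. The other 0.025 stays with the unrejected Step 5 hypothesis. After Step 9 the travelling 0.025 is free, but the plan does not use it.

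Either Step 5 hypothesis can be the loser. One is the primary endpoint in the secondary population; the other is a key secondary endpoint in the primary population. In the first case all four key secondary endpoints in all subjects can be declared while the exacerbation rate in the same population, at p = 0.03 for example, cannot. A better use of alpha would allow that declaration at the same overall error rate.

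**Working it through.** **Inputs.** Overall level 0.05 two-sided, Step 5 split and Step 6–9 levels: Section 8.5.1. Placebo rate 0.8 per year, dispersion 0.95, about 355 subject-years per group, 37% reduction: Section 8.2. The protocol gives no effect sizes for symptoms or the other key secondary endpoints, so those below are assumed.

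**The plan's own figures.** 0.05/2 = 0.025, as stated. Exposure: 770 × (1 − 0.15/2) = 712 subject-years, against about 710 stated. Power uses a Wald test on the log rate ratio:

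- variance = (1/0.8 + 1/(0.8 × 0.63) + 2 × 0.95)/355 = 5.134/355 = 0.01446, so SE = 0.1203
- standardised effect = |ln 0.63|/SE = 0.4620/0.1203 = 3.84
- power at the 1% level = Φ(3.84 − 2.576) = 0.897, which agrees with the stated 90%.

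**Tracing alpha through an example.** Take p = 0.01 for the biomarker positive symptom score, p = 0.03 for the all-subjects exacerbation rate and p = 0.01 at each of Steps 6–9. As written, everything is declared except the exacerbation rate. With the 0.025 returned after Step 9, the rate is tested at 0.025 + 0.025 = 0.05 and is declared. With the two Step 5 p-values swapped, the symptom score is lost in the same way.

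**Why the error rate allows the return.** A retest happens only after every other hypothesis in the sequence has been rejected.

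- If any of those others is a true null, a false rejection has already occurred, so the retest adds nothing to the family-wise error.
- If the retested hypothesis is the only true null, its error rate is at most 0.05.

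The maximum is therefore still 0.05. In graphical terms, let Step 9 pass half its level to each Step 5 hypothesis. Once one of these and Steps 6–9 are rejected, the weight to the other becomes (1/2)/(1 − 1/2) = 1, so it is tested at the full 0.05 under any dependence. A simulation over all 63 sets of true nulls among the six hypotheses (correlation 0 and 0.5) gave the same highest estimate, 0.052, with and without the return. With 40,000 draws each, the simulation error is √(0.05 × 0.95/40,000) = 0.001 per estimate, and this is the largest of many. The error rate for the retested hypothesis alone does change: when it is the only true null and everything else is rejected, it rises from 0.025 to 0.05.

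**Ceiling on the gain for the all-subjects exacerbation rate.** The same formula with the Section 8.2 inputs gives the following; reductions below 37% are assumed.

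| True reduction | Power at 0.025 | Power at 0.05 | Difference (points) |
|---|---|---|---|
| 20% | 0.380 | 0.491 | 11.0 |
| 25% | 0.590 | 0.695 | 10.5 |
| 30% | 0.783 | 0.857 | 7.3 |
| 37% | 0.945 | 0.970 | 2.5 |

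These are ceilings on the unconditional gain, because Steps 1–4, the symptom score in Step 5 and Steps 6–9 must also succeed. In observed terms, solving RR = exp(−z × SE) gives significance from a 22.9% observed reduction at 0.025 and from 20.2% at 0.05. Only results between those two are affected.

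**Gain given that Steps 1–4 succeed (simulated).** Assumed standardised effects were 2.0–3.0 for the Step 5 symptom score and 2.8–4 for Steps 6–9, with common correlation 0.3 or 0.5.

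- Symptom score, biomarker positive: about 1–9 points.
- Exacerbation rate, all subjects, at 20–30% reductions (standardised effects about 1.9–3.0): about 0.6–7 points.
- Exacerbation rate, all subjects, at the planned 37% (3.84): about 0.1–0.8 points.

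With every assumed input at its most favourable, the upper ends of the first two ranges rise by a few points; the figure at 37% stays under 1 point.

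**Unconditional gain.** With assumed effects of 2.0 or 2.8 at Steps 2–4, Steps 1–4 all succeeded in 18–59% of simulated trials. At roughly the planned exacerbation effect the unconditional gain is then 0.03–0.23 points for the exacerbation rate. It is about 0.6–4 points for the symptom score.

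**The case against.** The strongest reply is that nothing here is wrong. The sequence is valid and can be carried out as written, and a chain without a return loop is a legitimate choice. A sponsor may also not want the all-subjects exacerbation claim to depend on four secondary endpoints succeeding first. That stands, and it limits the point to an optional improvement. It does not show that the alpha is put to any use.

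It is also fair that the benefit to the exacerbation rate nearly vanishes at the planned effect, that it applies only after a long run of successes, and that the symptom score figures rest wholly on assumed effects.

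Two stronger readings are tempting, and the protocol supports neither.

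- A reader might infer that the claim of strong error control in Section 8.5.1 is false. It is not: unused alpha makes the procedure conservative.
- A reader might infer that the sequence conflicts with Section 8.1, which considers asthma control only after a significant exacerbation effect, and that returning alpha would cure this. Section 8.1 acts as a safeguard here and does not say in which population the condition applies. Key secondary endpoints in all subjects can be declared without the exacerbation rate because either Step 5 rejection opens Step 6. When the all-subjects exacerbation p-value exceeds 0.05, returning alpha changes nothing.

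**Conclusion.** The point holds as one of efficiency, and it is minor. The hierarchy controls the family-wise error rate but is not alpha-exhaustive: with exactly one Step 5 rejection and success at Steps 6–9, 0.025 of the 0.05 is left idle. The loss bites only when the unrejected Step 5 p-value lies above 0.025 and at or below 0.05. The likelier beneficiary is the biomarker positive symptom score. The all-subjects exacerbation rate gains noticeably only if the true reduction falls well short of 37%. The reading of the levels and the error-rate argument follow from the text of Section 8.5.1; the sizes of the gains depend on the assumed effects and correlations.

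**What to change.** Add to Section 8.5.1, and mirror in the SAP: *Step 10. If exactly one Step 5 hypothesis was rejected and Steps 6–9 were all significant at 0.025, the other Step 5 hypothesis is retested two-sided at 0.05.*

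The step only adds rejections, so no existing claim is lost. It needs no extra subjects, and the maximum family-wise error stays at 0.05. The price in error terms is the rise from 0.025 to 0.05 for the retested hypothesis when it alone is a true null.

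The administrative cost is more than one sentence. The hierarchy sits in the protocol, so a substantial change follows the amendment and approval route in Section 10.5. It must be final before unblinding, and time is short: this edition is dated 09 June 2017 and Section 9.3 expects the study to end by Q3 2017. Section 8.1 already foresees an SAP update before unblinding to define the biomarker positive population, and the change could be timed with it. If the sponsor prefers no return of alpha, a sentence saying that this is deliberate would settle the matter.

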### 8.5.2 Sensitivity analyses

The interpretation of exacerbation data post-discontinuation of treatment is likely to be confounded by reduced quality of objective confirmation of deterioration, and by the use of subsequent therapies. Sensitivity analyses for the primary endpoint will be carried out to explore the impact of this, e.g. exclusion of data post-discontinuation of treatment.

Sensitivity analyses for the primary endpoint and the key secondary endpoints based on different missing data mechanism assumptions including those expected to be more conservative such as missing not at random will be used to explore the robustness of any treatment effect, including multiple imputation approaches. Full details of the sensitivity analyses will be pre-specified in SAP and documented prior to database lock of the studies.

### **8.5.3 Subject disposition, demography data and subjects characteristics**

Subject disposition will be summarized using the all subjects analysis set.

The number of enrolled subjects will be summarized. The number and percentage of subjects within each treatment group will be presented by the following categories; randomized, not randomized (and reason), received study treatment, didn't receive study treatment (and reason), completed treatment, discontinued treatment (and reason), completed study, and discontinued study (including reason).

Demographic data such as age, gender, and race will be summarized by treatment group for the full analysis set and biomarker positive and negative populations.

Various baseline characteristics will also be summarized by treatment for the full analysis set. These include medical, surgical and respiratory disease histories, weight, height and BMI, smoking status, history of allergy, FEV1 (pre and post-BD) at baseline, asthma duration, age at onset of asthma, asthma medications, the number of asthma exacerbations in the previous 12 months, and the number of asthma exacerbations requiring hospitalizations in the previous 12 months.

Medical and surgical histories will be summarized by MedDRA Preferred Term (PT) within the System Organ Class (SOC) level of MedDRA.

The number and percentage of subjects who take concomitant medications, and those who take disallowed concomitant medications during the study, will be presented by treatment group. Concomitant medications will be classified according to the AstraZeneca Drug Dictionary. The summary tables will present data by generic term using Anatomical Therapeutic Chemical (ATC) classification system codes.

### **8.5.4 Exposure**

Exposure to IP will be summarized by treatment group, for the safety analysis set and biomarker positive and negative populations.

### **8.5.5 Violations and deviations**

Only important protocol deviations will be listed and tabulated in the CSR. Protocol deviations that may greatly impact the completeness, accuracy, and/or reliability of the study data or that may significantly affect a subject's rights, safety, or well-being include:

- Subjects who do not meet the inclusion criteria
- Subjects who do not meet the randomization criteria
- Subjects who meet any of the exclusion criteria
- Subjects who use one or more disallowed medication (for any reason, unless otherwise specified) during the randomized treatment period

- Subjects who received the incorrect study treatment or study dose at any time during the 52-week double-blind treatment period
- Subjects who developed withdrawal criteria during the study but were not withdrawn

### 8.5.6 Analysis of the primary variable

The primary efficacy variable is the AAER and the primary analysis is to compare the AAER for tralokinumab with placebo in the two subject populations based on the full analysis population ('all subjects' and biomarker positive population).

For each population the primary objective will be evaluated through the hypothesis test:

$H_0$ : rate ratio (tralokinumab/placebo) equals 1 vs.

$H_1$ : rate ratio does not equal 1.

The AAER in the tralokinumab group will be compared to that seen in the placebo group using a negative binomial model. The response variable in the model will be the number of asthma exacerbations experienced by a subject, over the 52-week double-blind treatment period. Covariates and factors included in the model will include at least treatment and the stratifying variables. The logarithm of the subject's corresponding follow-up time will be used as an offset variable in the model to adjust for subjects having different exposure times during which the events occur.

The standard parameterization approach (NB2) of the Negative Binomial model will be applied (Hilbe 2011).

The estimated treatment effect (i.e., the rate ratio of tralokinumab versus placebo), corresponding 95% confidence interval (CI), and two-sided p-value for the rate ratio will be presented. In addition, the AAER and the corresponding 95% CI within each treatment group will be presented.

The individual exacerbation criteria (ER or urgent care visits due to asthma that required systemic corticosteroids, hospitalization due to asthma, or use of systemic corticosteroids) will also be summarized descriptively.

### 8.5.7 Analysis of secondary variable(s)

All efficacy secondary objectives will be analyzed based on the full analysis population in both populations ('all subjects' and biomarker positive populations).

#### 8.5.7.1 Lung Function

**The key secondary outcome variable for lung function is:** Percent change from baseline in pre-dose/pre BD FEV1.

The percent change from baseline in pre-dose/pre-BD FEV1 at Week 52 will be compared between tralokinumab and placebo using a repeated measures analysis on all subjects with a baseline pre-dose/pre-BD FEV1 measurement in the full analysis set.

The dependent variable will be the percent change from baseline in pre-BD FEV1 at post-baseline protocol-specified visits (up to the EOT visit). Treatment group and the variables used in the stratified randomization will be included as independent variables. Visit will be fitted as a categorical variable, and the variance-covariance matrix will be assumed to be unstructured. If the procedure does not converge then a compound symmetric variance-covariance matrix will be used instead. The model is:

$$\text{Percent change in FEV1} = \text{Treatment group} + \text{stratifying variables} + \text{visit} + \text{treatment} * \text{visit}$$

Results will be presented in terms of LSMEANS, treatment differences in LSMEANS, 95% confidence intervals and p-values. Summary statistics of the change from baseline for all visits in the FEV1 at study site will be produced by treatment group.

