### **3.5 Methods for assigning treatment groups**

Randomization codes will be assigned strictly sequentially in each stratum as subjects become eligible for randomization.

The randomization code will be assigned from a randomization list prepared by an internal AstraZeneca computerized system (Grand). The randomization will be stratified by baseline serum periostin level ( $< 16.44$  ng/mL or  $\geq 16.44$  ng/mL) sampled during run-in, age (adult/adolescent) and geographical region (i.e. Asia Pacific, North America, South America, Central/Eastern Europe, and Western Europe/Rest of World). Stratified randomization is used to allow for evaluation within sub-groups and/or to allow for heterogeneity in placebo exacerbations rates (regions). Randomization will be done in blocks.

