## **8.4 Outcome measures for analyses**

### **8.4.1 General Definitions**

#### **8.4.1.1 Definition of baseline and subject baseline variables**

For spirometry variables the measurement recorded at the baseline visit (Visit 3) will be used as baseline. If the Visit 3 measurement is missing, the last non-missing value before Visit 3 will be used as baseline instead. For post-BD FEV1, the measurement after the first BD administration is the baseline.

The baseline for the ePRO variables (ACQ-6, AQLQ(s)+12, WPAI-CIQ, and EQ-5D-5L) will be captured on the ePRO device at Visit 3. Baseline for Asthma Daily Diary variables will be the bi-weekly mean for data collected between study day -14 and -1 (i.e. 14 to 1 day before Visit 3).

For laboratory data and physical examination, baseline will be defined as the latest non-missing assessment prior to first dose.

Absolute change from baseline outcome variables is computed as (post-randomization value – baseline value).

Percent change from baseline is computed as  $((\text{post-randomization value} - \text{baseline value}) / \text{baseline value}) \times 100\%$ . If either the post-randomization value or the baseline value is missing, then the absolute or percent change from baseline value will also be set to missing.

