#### 8.5.7.2 Asthma symptoms

**The key secondary outcome variable:** Change from baseline in bi-weekly mean daily asthma symptom score (combined daytime and night-time score as captured in the Asthma Daily).

The change from baseline in asthma symptom total score, daytime score, and night-time score at Week 52 will each be summarized and analyzed using the repeated measurement approach defined for change from baseline in pre-dose/pre-BD FEV1, as described in Section 8.4.2.4. Included in the model will also be the baseline mean daily asthma symptom score.

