#### 8.5.7.3 Asthma specific health-related quality of life

**The key secondary outcome variable:** Change from baseline in AQLQ(s)+12 total score.

The change in mean score from baseline for AQLQ(S)+12 at Week 52 will be summarized and analyzed using the repeated measurement approach defined for change from baseline in pre-dose/pre-BD FEV1, as described in Section 8.4.2.4. Included in the model will also be the baseline AQLQ(s)+12 total score.

**Supportive outcome variable:** AQLQ(S)+12 responder (yes/no)

Responder variables AQLQ(S)+12 (yes/no) will be analyzed using a logistic regression model with covariates of at least treatment, stratifying variables, and baseline value.

The number and percentage of subjects with AQLQ(s)+12 total score changes  $\geq 0.5$  will be summarized by treatment (identified as a large meaningful change). Additionally, the number and percentage of subjects achieving an improvement, no change, or deterioration will be summarized by treatment as per Section 8.4.3.5.

**Supportive outcome measure:** change from baseline to overall post-baseline mean of AQLQ(S)+12.

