#### 8.5.7.4 ACQ-6 defined asthma control

**The key outcome variable:** Change from baseline in ACQ-6.

Change in mean score from baseline for ACQ-6 will be summarized and analyzed using the repeated measurement approach defined for change from baseline in pre-dose/pre-BD FEV1, as described in Section 8.4.2.4. Included in the model will also be the baseline ACQ-6 mean score.

**Supportive outcome variable:** ACQ-6 responder (yes/no).

Responder variables ACQ-6 (yes/no) will be analyzed using a logistic regression model with covariates of at least treatment, stratifying variables, and baseline value.

The number and percentage of subjects achieving mean ACQ-6  $\leq 0.75$ ,  $0.75 < \text{mean ACQ-6} < 1.5$  and mean ACQ-6 of  $\geq 1.5$  at EOT will be summarized by treatment. Additionally, the number and percentage of subjects achieving an improvement, no change, or deterioration as per Section 8.4.3.4, ACQ-6 will also be summarized by treatment.

**Supportive outcome measure:** change from baseline to overall post-baseline mean of ACQ-6.

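### The FEV1 model for Step 2 leaves out baseline FEV1, although the other three key secondary models each adjust for their own baseline; the loss of precision is small but easily avoided

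*Protocol*

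**What the plan says.** Section 8.5.7.1 specifies "a repeated measures analysis on all subjects with a baseline pre-dose/pre-BD" FEV1 value. "Treatment group and the variables used in the stratified randomization will be included as independent variables", and the equation that follows contains treatment, the stratifying variables, visit and treatment by visit. Neither the text nor the equation has a baseline FEV1 term.

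The next three sections take over the same approach, and each adds a baseline:

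- Section 8.5.7.2, symptom score: "Included in the model will also be the baseline mean daily asthma symptom score".
- Section 8.5.7.3, AQLQ(S)+12: "Included in the model will also be the baseline AQLQ(s)+12 total score".
- Section 8.5.7.4, ACQ-6: "Included in the model will also be the baseline ACQ-6 mean score".

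On the baseline itself, Section 8.4.1.1 says: "For spirometry variables the measurement recorded at the baseline visit (Visit 3) will be used as baseline". Percent change is the difference from that value divided by that value. Under Section 3.5, "The randomization will be stratified by baseline serum periostin level", together with age group and region; no lung function measure is a stratum.

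Section 8.5.1 places FEV1 in the biomarker positive population at Step 2, tested at two-sided 0.05: "If a significant treatment effect is shown with regards to the primary endpoint in the biomarker positive population in Step 1". If Step 2 fails, testing stops. The synopsis sets treatment and the stratifying variables only as a minimum for the key secondary models.

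**The concern.** FEV1 is the only one of the four key secondary variables whose model lacks its own baseline, and the protocol gives no reason. Expressing the outcome as a percent change does not make the term redundant. One Visit 3 reading is both subtracted and used as the denominator, so a reading that is high by chance pushes percent change down, and a low one pushes it up. The result is a negative correlation with baseline that nothing else in the model absorbs.

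The randomized comparison does not depend on this term for its validity. What is at stake is precision, at a step on which all later confirmatory tests depend and in a subset of only 20% to 35% of the trial. Baseline FEV1 is not a stratification factor, so the model as written also makes no adjustment for a chance imbalance in it within that subset.

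**Working it through.** **Plan's own figure.** There is none to reproduce. The protocol gives no SD, target difference, power or interval width for FEV1.

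**Inputs from the protocol.** 770 subjects, 1:1; 20% to 35% biomarker positive; 15% loss to follow-up (Section 8.2).

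- Per arm: 770 × 0.20 / 2 = 77 and 770 × 0.35 / 2 = 134.75, about 135.
- Biomarker positive in total: 154 to about 270. After 15% loss, 154 × 0.85 ≈ 131.

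**Assumed input.** The correlation r of percent change with baseline FEV1, given the strata. It was simulated as follows:

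- baseline = true value + visit error;
- Week 52 = true value + individual change + visit error;
- mean 1.8 L; between-subject SD 0.45, 0.55 or 0.70 L; visit SD 0.15, 0.20 or 0.30 L; SD of true change 0, 0.15 or 0.25 L (27 combinations of 600,000 subjects);
- true FEV1 kept above 0.6 L and baseline above 0.8 L;
- assumed shifts in true FEV1 by age group, region and periostin.

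Without the strata, r ran from -0.08 to -0.36 (median r² 0.040). Given the strata it ran from -0.08 to -0.37 (r² 0.006 to 0.141, median 0.041).

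**Formulas.**

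- Interval width ratio: √(1 − r²). Net of one degree of freedom: √(1 − r²) × √((N − p)/(N − p − 1)), with p = 8 (intercept, treatment, age group, periostin, four region terms).
- Power, starting from 80%: Φ((1.960 + 0.842)/√(1 − r²) − 1.960).
- Equivalent extra subjects per arm: n × (1/(1 − r²) − 1).
- Half-width in percentage points, ignoring missing data: 1.96 × SD × √(2/n) × √(1 − r²), with SD assumed.

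**Central case, r² = 0.041.** √0.959 = 0.979, so the interval is 2.1% narrower. Net at N = 131: 0.9793 × √(123/122) = 0.983, or 1.7% narrower. Net at N = 270: 0.9793 × √(262/261) = 0.981, or 1.9% narrower. Power: Φ(2.802/0.979 − 1.960) = 81.6%.

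| | Low | Central | High |
|---|---|---|---|
| r² | 0.006 | 0.041 | 0.141 |
| Interval narrower, before df cost | 0.3% | 2.1% | 7.3% |
| Net, N = 131 | 0.1% wider | 1.7% | 6.9% |
| Net, N = 270 | 0.1% | 1.9% | 7.1% |
| Power, from 80% (before df cost) | 80.2% | 81.6% | 85.6% |
| Extra subjects per arm, n = 77 | 0.5 | 3.3 | 12.6 |
| Extra subjects per arm, n = 135 | 0.8 | 5.8 | 22.1 |
| Half-width, 77 per arm, SD 25 (7.90 without baseline) | 7.87 | 7.73 | 7.32 |
| Half-width, 135 per arm, SD 20 (4.77 without baseline) | 4.76 | 4.67 | 4.42 |

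**Cross-check by another route.** Suppose baseline and Week 52 FEV1 have equal SD on the log scale and correlation c with each other. Then |r| = √((1 − c)/2). For c = 0.80, 0.90 and 0.95 the interval narrows by 5.1%, 2.5% and 1.3%. If the Week 52 SD is 5% to 10% larger, the gain for c between 0.80 and 0.90 is about 0% to 3%. This agrees with a gain of about 2% in a central case.

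**The case against.** The strongest reply is that nothing is broken. The model as written gives an unbiased comparison with type I error controlled, and no stated design claim depends on the missing term. The synopsis treats the covariate list as a minimum, and the SAP, not seen here, may already include baseline. FEV1 is also scaled by its baseline, whereas the other three outcomes are absolute changes on bounded scores.

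The validity point stands in full; this is a matter of efficiency and consistency. The synopsis wording permits the term but does not supply it, and Section 8.5.7.1 presents its equation as complete. If the SAP does add baseline, the protocol and SAP would show different models for a confirmatory test and should be aligned. Scaling by baseline does not remove the dependence, because the same single reading enters twice.

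The objections to the size partly stand. The simulation's negative correlation follows from its assumption that true change is unrelated to true baseline, and the eligibility limits on FEV1 were not simulated. The two illustrative SDs have no basis in the protocol. One degree of freedom is spent, so at the low end there is essentially no gain, and with about 131 subjects the interval could even be slightly wider. Step 2 is also reached only after success at Step 1, for which the protocol quotes 70% to 90% power, so a shift of 1 to 2 power points is unlikely to decide the trial.

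**Conclusion.** The concern holds, as a small and avoidable loss of precision. The written FEV1 model omits its baseline, while the three models built on it each include theirs. In the central case the interval would be about 2% narrower, 1.7% to 1.9% after the degree of freedom, equivalent to about 3 subjects per arm at 77 or 6 at 135. The range over the simulated assumptions is from practically zero to about 7%; the cross-check favours roughly 0% to 5%. All of this rests on assumed FEV1 variability and on the resulting correlation. The absence of bias and of type I error inflation does not depend on those assumptions.

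**What to change.** In Section 8.5.7.1, add baseline pre-dose/pre-bronchodilator FEV1 as a continuous covariate. The model then reads: percent change in FEV1 on treatment, stratifying variables, baseline FEV1, visit and treatment by visit, with baseline by visit optional. Carry the same model into the SAP before unblinding, which Section 8.1 allows. Because Section 8.5.7.8 analyses home PEF with a similar model, say there whether baseline PEF is included as well.

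The cost is one model term and one degree of freedom. No visit, measurement or subject is added, and none is lost, because the analysis is already limited to subjects with a baseline FEV1.
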